#### **3.1.4. Safety Analysis Set**

The Safety Analysis Set includes all subjects who received at least 1 dose of study drug. This is the primary analysis set for safety analyses.

#### **3.1.5. Pharmacokinetic Analysis Set**

The Pharmacokinetic (PK) Analysis Set includes all subjects in the Safety Analysis Set who have at least 1 nonmissing plasma concentration data for filgotinib and/or its metabolite GS-829845. This is the primary analysis set for general PK analyses.

CCI

### 3.2. Subject Grouping

For analyses based on the All Randomized Analysis Set and FAS, subjects will be grouped according to the treatment to which they were randomized. For analyses based on the Safety Analysis Set and PP Analysis Set, subjects will be grouped according to actual treatment received. The actual treatment received will differ from the randomized treatment only when their actual treatment differs from randomized treatment for the entire treatment duration.

For the PK Analysis Set, subjects will be grouped according to the actual treatment they received.

### 3.3. Strata and Covariates

Subjects will be randomly assigned to treatment groups via the interactive web response system (IWRS) in a 2:1:1:2 ratio to filgotinib 200mg + MTX, filgotinib 100mg + MTX, filgotinib 200mg, and MTX using a stratified randomization schedule. Stratification will be based on the following variables:

- Geographic region (**Group A** includes the following countries: Australia, Belgium, Canada, France, Germany, Ireland, Israel, Italy, Netherlands, New Zealand, Republic of Korea, Singapore, South Africa, Spain, Sweden, Switzerland, United Kingdom, and USA; **Group B** includes the following countries: Bulgaria, Croatia, Czech Republic, Estonia, Georgia, Hungary, India, Latvia, Moldova, Poland, Romania, Russia, Serbia, Slovakia, and Ukraine; **Group C** includes the following countries: Argentina, Brazil, Chile, Colombia, Mexico, Peru, and Puerto Rico; **Group E** includes Japan; **Group D** includes the following countries/regions China (was originally planned but no subjects were screened or enrolled from this region), Hong Kong, Malaysia, Philippines, Taiwan, Thailand, and Vietnam.
- Presence of RF or anti-CCP Ab (Yes or No) (Presence of RF = No if RF < 15 IU/mL; Presence of anti-CCP Ab = No if anti-CCP Quant < 17 U/mL)

If there are discrepancies in stratification factor values between the IWRS and the clinical database, the values recorded in the clinical database will be used for analyses.

For efficacy endpoints, stratification factors and the baseline value of the efficacy variable(s) will be included as covariates in the efficacy analysis model, as specified in Section 6.

### 3.4. Examination of Subject Subgroups

The primary and key secondary efficacy endpoints will be examined using the following subgroups (but not limited to the ones listed below):

- Age (on the first dosing date of any study drug, < 65 or ≥ 65)
- Sex at birth (male, female)
- Race
- Baseline weight ( < 60 kg, ≥ 60 to < 100 kg, ≥ 100 kg)
- Geographic region (A, B, C, or E)
- Presence of RF or anti-CCP Ab (Yes or No)
- Duration of RA diagnosis on the first dosing date of any study drug (< 1 year, ≥ 1 to < 2 years, ≥ 2 years)
- Disease activity at Baseline (DAS28[CRP] ≤ 5.1 or DAS28[CRP] > 5.1)
- Concurrent use of oral systemic corticosteroids on the first dosing date of any study drug (Yes or No)
- High-sensitivity C-reactive protein (hsCRP) at baseline (≥ 4 mg/L, < 4 mg/L)

Lists of oral systemic corticosteroids are provided in [Appendix 1](#).

### 3.5. Multiple Comparisons

The primary endpoint for the study is the proportion of subjects who achieve ACR20 response at Week 24. The primary analyses will consist of a superiority test of filgotinib 200 mg in combination with MTX compared to MTX alone based on the ACR20 response rate at Week 24.

The following hypothesis testing for secondary analyses will commence after the primary analysis reaches statistical significance, and will be tested according to the hierarchical testing principle at the 2-sided 0.05 level. If a null hypothesis is not rejected, formal sequential testing will be stopped and only nominal significance will be reported for the remaining hypotheses:

- 1) Superiority of filgotinib 100 mg in combination with MTX compared to MTX alone based on ACR20 response rate at Week 24.
- 2) Superiority of filgotinib 200 mg in combination with MTX compared to MTX alone based on the change from Baseline in HAQ-DI at Week 24.
- 3) Superiority of filgotinib 100 mg in combination with MTX compared to MTX alone based on the change from Baseline in HAQ-DI at Week 24.

- 4) Superiority of filgotinib 200 mg in combination with MTX compared to MTX alone based on the change from Baseline in mTSS at Week 24.
- 5) Superiority of filgotinib 100 mg in combination with MTX compared to MTX alone based on the change from Baseline in mTSS at Week 24.
- 6) Superiority of filgotinib 200 mg alone compared to MTX alone based on ACR20 response rate at Week 24.
- 7) Superiority of filgotinib 200 mg alone compared to MTX alone based on the change from Baseline in HAQ-DI to Week 24.
- 8) Superiority of filgotinib 200 mg in combination with MTX compared to MTX alone based on the proportion of subjects with DAS28(CRP) < 2.6 at Week 24.
- 9) Superiority of filgotinib 100 mg in combination with MTX compared to MTX alone based on the proportion of subjects with DAS28(CRP) < 2.6 at Week 24.
- 10) Superiority of filgotinib 200 mg alone compared to MTX alone based on the proportion of subjects with DAS28(CRP) < 2.6 at Week 24.
- 11) Superiority of filgotinib 200 mg alone compared to MTX alone based on the change from Baseline in mTSS at Week 24.
- 12) Superiority of filgotinib 200 mg in combination with MTX compared to MTX alone based on the change from Baseline in SF-36 physical component score (PCS) at Week 24.
- 13) Superiority of filgotinib 100 mg in combination with MTX compared to MTX alone based on the change from Baseline in SF-36 PCS at Week 24.
- 14) Superiority of filgotinib 200 mg alone compared to MTX alone based on the change from Baseline in SF-36 PCS at Week 24.
- 15) Superiority of filgotinib 200 mg in combination with MTX compared to MTX alone based on the change from Baseline in FACIT-Fatigue at Week 24.
- 16) Superiority of filgotinib 100 mg in combination with MTX compared to MTX alone based on the change from Baseline in FACIT-Fatigue at Week 24.
- 17) Superiority of filgotinib 200 mg alone compared to MTX alone based on the change from Baseline in FACIT-Fatigue at Week 24.

### **3.6. Missing Data and Outliers**

#### **3.6.1. Missing Data**

In general, missing data will not be imputed unless methods for handling missing data are specified. Exceptions are presented in this document.

For missing last dosing date of study drug, imputation rules are described in Section 4.2.1. For partial date of initial RA diagnosis, imputation rules are described in Section 5.2. The handling of missing or incomplete dates for AE onset is described in Section 7.1.5.2, and for prior and concomitant medications in Section 7.4. Imputation rules adopted in the efficacy analyses are specified in Section 6.

#### **3.6.2. Outliers**

Outliers will be identified during the data management and data analysis process, but no sensitivity analyses will be conducted. All data will be included in the data analyses.

### **3.7. Data Handling Conventions and Transformations**

In general, age (in years) on the date of the first dose of study drug will be used for analyses and presentation in listings. If an enrolled subject was not dosed with any study drug, the randomization date will be used instead of the first dosing date of study drug. For screen failures, the date the last informed consent was signed will be used for age calculation. If only birth year is collected on the CRF, “01 July” will be used for the unknown birth day and month for the purpose of age calculation. If only birth year and month are collected, “01” will be used for the unknown birth day.

Non-PK Data that are continuous in nature but are less than the lower limit of quantitation (LOQ) or above the upper LOQ will be imputed as follows:

- A value that is 1 unit less than the LOQ will be used to calculate descriptive statistics if the datum is reported in the form of “< x” (where x is considered the LOQ). For example, if the values are reported as < 50 and < 5.0, values of 49 and 4.9, respectively, will be used to calculate summary statistics. An exception to this rule is any value reported as < 1 or < 0.1, etc. For values reported as < 1 or < 0.1, a value of 0.9 or 0.09, respectively, will be used for calculate summary statistics.
- A value that is 1 unit above the LOQ will be used to calculate descriptive statistics if the datum is reported in the form of “> x” (where x is considered the LOQ). Values with decimal points will follow the same logic as above.
- The LOQ will be used to calculate descriptive statistics if the datum is reported in the form of “≤ x” or “≥ x” (where x is considered the LOQ).

Natural logarithm transformation will be used for plasma/blood concentrations and analysis of PK parameters. Plasma concentration values that are below the limit of quantitation (BLQ) will be presented as “BLQ” in the concentration data listing. Values that are BLQ will be treated as 0 at predose time points, and one-half the value of the LOQ at postbaseline time points.

The following conventions will be used for the presentation of summary and order statistics:

- If at least 1 subject has a concentration value of BLQ for the time point, the minimum value will be displayed as “BLQ.”
- If more than 25% of the subjects have a concentration data value of BLQ for a given time point, the minimum and Q1 values will be displayed as “BLQ.”
- If more than 50% of the subjects have a concentration data value of BLQ for a given time point, the minimum, Q1, and median values will be displayed as “BLQ.”
- If more than 75% of the subjects have a concentration data value of BLQ for a given time point, the minimum, Q1, median, and Q3 values will be displayed as “BLQ.”
- If all subjects have concentration data values of BLQ for a given time point, all order statistics (minimum, Q1, median, Q3, and maximum) will be displayed as “BLQ.”

PK parameters that are BLQ will be imputed as one-half LOQ before log transformation or statistical model fitting.

### **3.8. Analysis Visit Windows**

#### **3.8.1. Definition of Study Day**

The first dose date of individual study drug will be calculated separately for each study drug (ie, filgotinib 200 mg, filgotinib 100 mg, MTX, and PTMs) in a treatment group. Study Day 1 is defined as the first dose date of any study drug, which is the minimum of the first dose dates of individual study drugs in a treatment group.

The last dose date of individual study drug will be calculated separately for each study drug in a treatment group. The last dose date for an individual study drug will be the end date on study drug administration CRF for the record where the “study drug was permanently withdrawn” flag is “Yes”. The last dose date of any study drug will be defined as the maximum of the last dose dates of individual study drugs in a treatment group.

Study Day will be calculated from the Study Day 1 and derived as follows:

- For postdose study days: Assessment Date – Study Day 1 + 1
- For days prior to the first dose: Assessment Date – Study Day 1

### 3.8.2. Analysis Visit Windows

Subject visits may not occur on protocol-specified days. Therefore, for the purpose of analysis, observations will be assigned to analysis windows.

In general, the baseline value will be the last nonmissing value on or prior to the first dose date of study drug, except for the mTSS baseline value. The mTSS baseline value will be derived based on the measurements collected on or prior to the first dose date of study drug + 14 days given the potential delay in scheduling an x-ray assessment..

For efficacy endpoints, vital signs, electrocardiogram (ECG), weight, lipid, and safety laboratory data, the analysis visit windows will be applied to data collected during the ‘on-treatment’ period. The ‘on-treatment’ period is defined as the last dose date of any study drug plus 7 days.

The analysis windows for on-treatment efficacy endpoints including joint count assessment, HAQ-DI (including subject’s pain assessment), subject’s global assessment (SGA), physician’s global assessment (PGA), serum CRP, CCI [REDACTED] and vital signs, weight, and safety laboratory data (lipid data excluded) are provided in [Table 3-1](#).

**Table 3-1. Analysis Visit Windows for On-treatment Joint Count Assessment, HAQ-DI, SGA, PGA, CRP, CCI [REDACTED] and Vital Signs, Weight, and Safety Laboratory Data (Lipid Data Excluded)**

Analysis Visit	Nominal Study Day	Lower Limit	Upper Limit
Baseline	1	(none)	1
Week 2	15	2	22
Week 4	29	23	43
Week 8	57	44	71
Week 12	85	72	99
Week 16	113	100	127
Week 20	141	128	155
Week 24	169	156	190
Week 30	211	191	232
Week 36	253	233	281
Week 44	309	282	337
Week 52	365	338	≥ 365

The analysis windows for on-treatment ECG data are provided in [Table 3-2](#).

**Table 3-2. Analysis Visit Windows for On-Treatment ECG Data**

Analysis Visit	Nominal Study Day	Lower Limit	Upper Limit
Baseline	1	(none)	1
Week 12	85	2	127
Week 24	169	128	211
Week 36	253	212	309
Week 52	365	310	≥ 365

The analysis windows for on-treatment lipid data are provided in [Table 3-3](#).

**Table 3-3. Analysis Visit Windows for On-Treatment Lipid Data**

Analysis Visit	Nominal Study Day	Lower Limit	Upper Limit
Baseline	1	(none)	1
Week 12	85	2	127
Week 24	169	128	267
Week 52	365	268	≥ 365

The analysis windows for on-treatment mTSS data are provided in [Table 3-4](#).

**Table 3-4. Analysis Visit Windows for On-treatment mTSS Data**

Analysis Visit	Nominal Study Day	Lower Limit	Upper Limit
Baseline	1	(none)	14
Week 24	169	15	267
Week 52	365	268	≥ 365

The analysis windows for on-treatment SF-36, FACIT-Fatigue, EQ-5D and WPAI-RA are provided in [Table 3-5](#). The analysis windows for on-treatment Healthcare Resource Utilization Questionnaire (HRUQ) and Treatment Satisfaction Questionnaire for Medication (TSQM) are provided in [Table 3-6](#).

**Table 3-5. Analysis Visit Windows for On-treatment SF-36, FACIT-Fatigue, EQ-5D, and WPAI-RA**

Analysis Visit	Nominal Study Day	Lower Limit	Upper Limit
Baseline	1	(none)	1
Week 4	29	2	57
Week 12	85	58	127
Week 24	169	128	211
Week 36	253	212	309
Week 52	365	310	≥ 365

**Table 3-6. Analysis Visit Windows for On-Treatment HRUQ and TSQM**

Analysis Visit	Nominal Study Day	Lower Limit	Upper Limit
Baseline	1	(none)	1
Week 12	85	2	127
Week 24	169	128	211
Week 36	253	212	309
Week 52	365	310	≥ 365

Vital signs, weight, ECGs, lipids, and safety laboratory data collected in the posttreatment followup period will also be summarized. The analysis window for posttreatment followup period is defined as from (the last dose date of any study drug + 8 days) to (the last dose date of any study drug + 30 days). If multiple valid, nonmissing measurements exist in the posttreatment followup visit window, then the latest record will be selected for analysis. If the chronological order cannot be determined (eg, more than 1 record on the same day with time missing), for any given subject, the value with the worst severity will be selected for categorical variable, and the average will be taken for continuous variable. Data obtained after last dose date plus 30 days will be excluded from the summaries, but will be included in the listings.

For efficacy endpoints, the same analysis visit windows will be applied to all available data collected during standard of care.

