For a complete list of study inclusion and exclusion criteria, please refer to Sections 4.2 and 4.3.

Main Eligibility Criteria

- 1) Male or female subjects who are ≥18 years of age, on the day of signing informed consent
- 2) Have a diagnosis of RA (2010 ACR/ EULAR criteria), and are ACR functional class I-III
- 3) Have ≥6 swollen joints (from a SJC66) and ≥6 tender joints (from a TJC68) at Screening and Day 1

- 4) Must meet at least one of the following parameters at Screening:
 - positivity for either RF or anti-CCP Ab per central laboratory
 - OR
 - Serum CRP \geq 4 mg/L based on central laboratory value
 - OR
 - \geq 1 documented joint erosion on radiographs of the hands, wrists or feet by central reading
- 5) Limited or no prior treatment with MTX, ie, no more than 3 doses of MTX \leq 25 mg each in their lifetime for the treatment of RA, with last dose at least 28 days prior to Day 1, and are an appropriate candidate for MTX therapy, as per investigator judgment

Study Procedures/
Frequency:

The subjects will visit the clinical study center at Screening, Day 1, Weeks 2, 4, 8, 12, 16, 20, 24, 30, 36, 44, and 52 or ET.

For those subjects not entering the LTE, a follow-up visit will be planned 4 weeks after the last dose of study drug (Post Treatment Week 4). Consequently, subjects are planned to be in the study for approximately 60 weeks.

During the Screening period, the subject's radiographs (hands, wrists, and feet) will be sent for blinded central scoring. In addition, information on demographics, medical history/concomitant diseases, prior and current RA medications will be collected. A physical examination, a 12-lead electrocardiogram (ECG), and clinical laboratory assessments will be conducted to determine the subject's eligibility for study participation. The screening window may be extended to up to 42 days prior to the Day 1 visit for subjects who require repeat collection of radiographs only.

At Day 1, after the subject's eligibility for the study has been confirmed, the subject will be randomized to receive one of 4 dosing regimens: filgotinib 200 mg q.d. plus MTX up to 20 mg weekly, filgotinib 100 mg q.d. plus MTX up to 20 mg weekly, filgotinib monotherapy 200 mg q.d. or MTX monotherapy up to 20 mg weekly.

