On-treatment assessments will include: adverse events (AEs), concomitant medications, review of study medication compliance through drug accountability, SJC66, TJC68, Subject's Global Assessment, Subject's Pain Assessment, HAQ-DI, Functional Assessment of Chronic Illness Therapy-Fatigue (FACIT-Fatigue), Short-Form Health Survey (SF-36), Work Productivity and Activity Impairment- Rheumatoid Arthritis (WPAI-RA), EuroQol 5 Dimensions (EQ-5D), CCI [REDACTED] Treatment Satisfaction Questionnaire for Medication (TSQM), Healthcare Resource Utilization, Physician's Global Assessment, physical examination, weight, vital signs, serum CRP, blood and urine sampling for safety laboratory tests and biomarkers at selected visits, and urine pregnancy tests (females of child bearing potential only).

A resting 12-lead ECG should be performed at Screening, Weeks 12, 24, 36, and 52 or ET, and at the Post-treatment Week 4 follow-up visit. ECGs should be interpreted by the investigator (or qualified designee) for clinical significance.

For all subjects, blood samples for PK analysis should be collected at least 30 minutes post study drug dose on Week 4, prior to study drug administration on Weeks 12 and 24, and any time at the final assessment visit on Week 52 or ET.

CCI [REDACTED]

Blood samples for biomarker analysis should be collected at Day 1, Weeks 4, 8, 12, 24, 36, and Week 52 or ET and urine samples should be collected at Day 1, Weeks 12, 24, and Week 52 or ET.

Radiographs of the bilateral hands, wrists, and feet should be taken at Screening, Week 24, and Week 52 or ET. However, if a subject prematurely discontinues study participation and has had X-rays performed within the previous 12 weeks, then X-rays do not need to be repeated at the ET visit. Radiographs performed after enrollment may be done +/-7 days of the scheduled visit.

Post treatment follow-up assessments include AEs, concomitant medications, physical examination, 12-lead ECG, weight, vital signs, blood and urine sampling for safety laboratory tests, and urine pregnancy tests (females of child bearing potential only).

CCI

[REDACTED]

Test Product, Dose, and Mode of Administration:	200 mg filgotinib orally q.d. plus MTX weekly up to 20 mg 100 mg filgotinib orally q.d. plus MTX weekly up to 20 mg 200 mg filgotinib orally q.d.
--	---

Reference Therapy, Dose, and Mode of Administration:	MTX weekly up to 20 mg or PTM MTX weekly PTM filgotinib 200 mg orally q.d. PTM filgotinib 100 mg orally q.d.
---	--

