6.5. Week 52/Early Termination (ET)

If a subject discontinues the study, every attempt should be made to perform the required study-related ET and Post Treatment Week 4 visits and procedures.

Subject's Global Assessment, HAQ-DI and Pain Scale, FACIT- Fatigue, and SF-36 are recommended to be done before any other study procedures. Invasive study procedures such as blood draws should be done at the end of a study visit.

- Subject's global assessment
- HAQ-DI and Pain Scale
- FACIT-Fatigue and SF-36,
- WPAI-RA and EQ-5D, where available

- TSQM, when and where available
- Healthcare resource utilization questionnaire
- Complete physical examination
- Weight
- Vital signs
- SJC66/TJC68
- Physician's global assessment
- 12-Lead ECG
- Radiographs of hands, wrists, and feet

- Obtain blood samples for:
 - Hematology and Serum Chemistry
 - Lipid profile (fasting)
 - Serum CRP
 - Pregnancy test (serum required if subject is entering into LTE)
 - Blood sampling for PK
 - Biomarker blood samples
 - Quantitative Ig
 - vfpBMC and leukocyte subset samples (US and Canada only)
- Urinalysis (including pregnancy test if applicable)
- Urine stored for biomarker analysis
- Assessment of AE(s)/serious (S)AE(s) and concomitant medication
- Review Entry criteria for LTE (if applicable)

6.6. Post Treatment Week 4

The following procedures will be completed 4 weeks after the subject's last dose of study treatment. This visit is not applicable if the subject is continuing onto the LTE study.

- Symptom-driven physical examination
- Weight
- Vital signs
- Urinalysis (including pregnancy test if applicable)
- 12-lead ECG
- Obtain blood samples for:
 - Hematology and Serum Chemistry
- Urinalysis
- Assessment of AE(s)/SAE(s) and concomitant medication

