Appendix 2. Study Procedures Table

EVENT		Screening ^a	Treatment Period												Follow-Up ^d
Visits	Day 1 ^b		W2	W4	W8	W12	W16	W20	W24	W30	W36	W44	W52/ ET ^c	Post Treatment Week 4	
Visit window (Days)	(±3 days)		(±3 days)	(±3 days)	(±3 days)	(±3 days)	(±3 days)	(±3 days)	(±3 days)	(±3 days)	(±7 days)	(±7 days)	(±7 days)	(±7 days)	(±7 days)
Screening Assessments	Informed Consent	X													
	Inclusion/Exclusion Criteria	X	X ^e												
	Demographics and Baseline Disease Characteristics	X													
	RA diagnosis and Prior RA Treatment, Medical History ^f	X													
	Complete Physical Examination ^g	X							X				X		
	TB test and Chest X-Ray ^h	X													
	RF/anti-CCP Ab	X													

EVENT		Screening ^a	Treatment Period												Follow-Up ^d
			Day 1 ^b	W2	W4	W8	W12	W16	W20	W24	W30	W36	W44	W52/ ET ^c	Post Treatment Week 4
Visits	Visit window (Days)			(±3 days)	(±3 days)	(±3 days)	(±3 days)	(±3 days)	(±3 days)	(±3 days)	(±7 days)	(±7 days)	(±7 days)	(±7 days)	(±7 days)
Patient Questionnaires	Subject's global assessment ⁱ	X	X	X	X	X	X	X	X	X	X	X	X	X	
	HAQ-DI and Pain Scale ⁱ	X	X	X	X	X	X	X	X	X	X	X	X	X	
	FACIT-Fatigue, SF-36, WPAI-RA, EQ-5D ¹		X		X		X			X		X		X	
	Healthcare Resource Utilization Questionnaire and TSQM ¹		X				X			X		X		X	
CCI															
Physical Exam and Provider Assessments	Physician's global assessment	X	X	X	X	X	X	X	X	X	X	X	X	X	
	Vital signs ^j	X	X	X	X	X	X	X	X	X	X	X	X	X	X
	Symptom-driven physical examination		X	X	X	X	X	X	X		X	X	X		X
	12-Lead ECG	X				X			X		X		X		X
	SJC66/TJC68	X	X	X	X	X	X	X	X	X	X	X	X	X	
	Weight	X	X	X	X	X	X	X	X	X	X	X	X	X	X

EVENT		Screening ^a	Treatment Period												Follow-Up ^d
Visits	Day 1 ^b		W2	W4	W8	W12	W16	W20	W24	W30	W36	W44	W52/ ET ^c	Post Treatment Week 4	
Visit window (Days)			(±3 days)	(±3 days)	(±3 days)	(±3 days)	(±3 days)	(±3 days)	(±3 days)	(±7 days)	(±7 days)	(±7 days)	(±7 days)	(±7 days)	
Laboratory Assessments	Pregnancy test ^k	X	X	X	X	X	X	X	X	X	X	X	X	X	
	Hematology and Chemistry ^l	X	X	X	X	X	X	X	X	X	X	X	X	X	
	Serum CRP	X	X	X	X	X	X	X	X	X	X	X	X		
	Urinalysis and urine for biomarkers ^m	X	X				X			X				X	
	Quantitative IG	X							X				X		
	Endocrine: FSH, TSH, and HbA1c	X													
	Lipid profile (fasting) ^l		X				X		X				X		
	CCI														
	PK blood samples ^o				X		X			X				X	
	Biomarker Blood Samples: Plasma biomarker, serum biomarker, transcriptome, TCR/BCR repertoire ^p		X		X	X	X			X		X		X	
	vfPBMC and Leukocyte subset ^q		X		X	X	X			X		X		X	

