### **7.2.2.1. Treatment-Emergent Laboratory Abnormalities**

Treatment-emergent laboratory abnormalities are defined as values that increase at least 1 toxicity grade from baseline at any postbaseline time point, up to and including the date of last dose of any study drug plus 30 days for subjects who permanently discontinued study drug, or the last available date in the database snapshot for subjects who were still on treatment at the time of an interim analysis.

If the relevant baseline laboratory value is missing, any abnormality of at least Grade 1 observed within the time frame specified above will be considered treatment emergent.

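### The SAP's post-treatment summary window ends 30 days after the last dose, but the follow-up visit may validly take place up to Day 35

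*SAP*

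**What the plan says.** Days below are counted from the last dose of any study drug.

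**Visit schedule.** The protocol synopsis says that, for subjects not entering the extension study, "a follow-up visit will be planned 4 weeks after the last dose of study drug (Post Treatment Week 4"). Protocol 6.6 repeats the timing: "The following procedures will be completed 4 weeks after the subject's last dose of study treatment". In Appendix 2 the column headed "Post Treatment Week 4" carries a window of ±7 days. The synopsis lists what is done there: "Post treatment follow-up assessments include AEs, concomitant medications, physical examination, 12-lead ECG, weight, vital signs, blood and urine sampling for safety laboratory tests". Footnote d of Appendix 2 restricts the visit to subjects who leave the study early and to Week 52 completers who do not enter the extension.

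**Analysis window.** SAP 3.8.2 states: "Vital signs, weight, ECGs, lipids, and safety laboratory data collected in the posttreatment followup period will also be summarized". The window runs from "the last dose date of any study drug + 8 days) to (the last dose date of any study drug + 30 days", and where several valid records fall inside it the latest is used. For anything later, "Data obtained after last dose date plus 30 days will be excluded from the summaries, but will be included in the listings".

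**Other uses of 30 days.** Protocol 8.6 sets the same limit for summaries of safety data, with room for exceptions to be specified. SAP 7.2 applies it to laboratory summaries. SAP 7.2.2.1 applies it to treatment-emergent laboratory abnormalities: "up to and including the date of last dose of any study drug plus 30 days for subjects who permanently discontinued study drug". SAP 7.2.3 and the TEAE definition (Protocol 8.6.2, SAP 7.1.5.1) use it as well. SAP 7.7 declares no departure from the protocol's safety analyses.

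**The concern.** A visit summary should cover the days on which the protocol allows the visit. Here it does not: a site that sees a subject on Day 33 has followed the protocol, yet the ECG, vital signs, weight, hematology and chemistry from that visit enter no summary table.

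There is a second effect. The window opens at Day 8 and takes the latest record inside it. If a subject has an unscheduled or early-termination record on, say, Day 10 and the scheduled follow-up on Day 33, the table shows the Day 10 value as the post-treatment value. The preference for the latest record is then defeated by the cut-off.

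What is at stake is the completeness of the post-treatment safety tables, in a group already reduced because extension entrants do not have this visit.

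**Working it through.** **Inputs**
- Planned visit: 4 weeks after the last dose (Protocol synopsis and 6.6).
- Visit window: ±7 days (Protocol Appendix 2, follow-up column).
- Summary window: Day 8 to Day 30 (SAP 3.8.2).

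The 30-day limit is a convention; neither document derives it, so there is no figure to reproduce.

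**Calendar arithmetic**
- Nominal visit day: 4 × 7 = 28.
- Permitted days: 28 − 7 = 21 to 28 + 7 = 35, which is 35 − 21 + 1 = 15 days.
- Permitted but not summarized: Days 31, 32, 33, 34 and 35, which is 5 days.
- Share of permitted days: 5/15 = 33.3%.
- With an upper limit of Day 35: 0 of 15 excluded.

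**Share of visits, under assumed timing.** The documents do not say when visits occur inside the window. If every permitted day is equally likely, the loss is 33%. Otherwise, take visit day as normal with mean μ and SD σ, rounded to whole days and truncated to Days 21 to 35:

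share = [Φ((35.5 − μ)/σ) − Φ((30.5 − μ)/σ)] / [Φ((35.5 − μ)/σ) − Φ((20.5 − μ)/σ)]

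Example, μ = 28, σ = 3: [Φ(2.50) − Φ(0.83)] / [Φ(2.50) − Φ(−2.50)] = (0.994 − 0.798)/(0.994 − 0.006) = 0.199.

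| Assumed centre | SD 2 | SD 3 | SD 4 | SD 5 |
|---|---|---|---|---|
| Day 28 | 10.6% | 19.9% | 25.1% | 27.9% |
| Day 29 | 22.6% | 29.9% | 32.4% | 33.2% |
| Day 30 | 40.0% | 41.5% | 40.3% | 38.8% |

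The result depends more on whether visits run late than on their spread.

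**What the limit touches.** ECG, vital signs, weight, hematology and chemistry are scheduled at this visit and summarized under SAP 3.8.2. Lipids are named in the SAP window but are not scheduled at this visit.

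**The case against.** The strongest reply is that 30 days is the plan's declared safety reporting period. Protocol 8.6 sets it for summaries, Protocol 7.3 for AE collection, Protocol 8.6.2 and SAP 7.1.5.1 for TEAEs, and SAP 7.2 to 7.2.3 for laboratory data. This stands. A reader might infer that the SAP has departed from the protocol, but the SAP follows Protocol 8.6. That section and the Appendix 2 visit window do not fit each other. Because Protocol 8.6 allows exceptions, the SAP may resolve the conflict without a protocol amendment.

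The second reply is that nothing is discarded. This also stands: the later values are listed, and SAP 7.2 flags out-of-range and graded laboratory results in the listings. Listings do not, however, give a comparison by treatment group.

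Three further inferences are tempting and are not supported.
- *That this is the only planned off-drug measurement for most subjects.* Extension entrants do not have the visit, and the documents do not say how many will enter. Subjects who stop drug for non-response or loss of response continue study visits (Protocol 3.2), and other discontinuers are encouraged to (Protocol 3.5.2).
- *That Days 31 to 35 hold the best evidence of recovery after washout.* Protocol 1.2.3 reports dose-dependent neutrophil, platelet and creatinine changes, but no visible objective or endpoint concerns reversal, and nothing shows that these days differ from Days 21 to 30. Subjects who stop permanently also move to standard-of-care treatment, so later values need not be cleaner.
- *That the rule biases the comparison.* The documents give no reason to expect visit timing to differ by arm. The likelier effect is fewer summarized subjects and an occasional substituted earlier record.

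**Conclusion.** The mismatch is real and follows from the documents' own figures: five of the 15 days on which the follow-up visit is permitted lie beyond the summary window. The share of visits lost is an assumption. It is about 11% to 28% with visits centred on Day 28 (SD 2 to 5 days), 33% with uniform timing, and about 39% to 42% with visits centred on Day 30. How often an earlier record would replace the scheduled one cannot be estimated from the documents.

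The consequence is modest. It concerns descriptive safety tables, only in subjects who have this visit, and the primary analysis, type I error and power are untouched.

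A reader might also infer that the treatment-emergent laboratory definitions should move to Day 35. A laboratory abnormality first seen on Days 31 to 35 is indeed outside those counts. But AE collection and TEAEs end at Day 30, so extending only the laboratory definition would count a Day 33 abnormality as treatment-emergent while a related AE would not count. The documents do not show that trade to be better, so the conclusion is confined to the visit summaries.

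**What to change.** 1. In SAP 3.8.2, set the upper limit of the post-treatment follow-up summary to last dose + 35 days for vital signs, weight, ECG and safety laboratory data.
2. In SAP 7.2, align the limit for the by-visit laboratory summaries (SAP 7.2.1), worded so that it does not carry over to the abnormality tables.
3. Keep 30 days for TEAEs and for the laboratory abnormality analyses in SAP 7.2.2 and 7.2.3, so that these stay aligned.
4. In SAP 7.7, note that the longer visit-summary window uses the exception allowed by Protocol 8.6.

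The cost is a few lines of SAP text and one programming limit. The downside is that the visit-summary cut-off will differ by 5 days from the treatment-emergent cut-off, which needs a table footnote. Because the window works by date, any other record from Days 31 to 35 in a subject who stopped drug but stayed in the study would also enter the summary.
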